2.2.5 Withdrawal of informed consent

Any data collected in the clinical database after a subject withdraws informed consent from all further participation in the trial, will not be included in the analysis datasets. The date on which a patient withdraws full consent will be recorded in the eCRF.

Third party data e.g. PK, biomarker etc. collected in the clinical database without having obtained consent for collection will not be included in the analysis datasets. These data will be excluded by the presence of the appropriate protocol deviation criterion.

2.3 Patient disposition, demographics and other baseline characteristics

2.3.1 Demographics and baseline characteristics

Demographic and other baseline data will be summarized descriptively for the FAS and the safety set (if not the same).

Categorical data will be presented as frequencies and percentages. For continuous data, mean, standard deviation, median, minimum, and maximum will be presented. For selected parameters, 25th and 75th percentiles will also be presented.

Demographic variables include Age (in year), Age category (< 65/≥ 65), gender, race, and ethnicity.

Baseline disease characteristics include time to first LCI699 dose since diagnosis of Cushing's disease, Cushing's disease status (de novo or persistent/recurrent), use of previous treatment, or surgery, mean UFC at baseline.

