1.1.2 Period 1 (Weeks 1-12): double-blind, placebo-controlled period

This is the randomized, double-blind, placebo-controlled period (Weeks 1-12). Eligible patients are randomized in a 2:1 ratio to treatment with study drug (osilodrostat or placebo, respectively). Patients are stratified at randomization according to history of pituitary irradiation (yes/no). Study visits occur at Weeks 2, 5, 8, and 12 (Figure 1-2). Study drug is started on Day 1 at a dose of 2 mg b.i.d., and titrated according to the regimen described in protocol Section 6.2, to a dose which lowers mUFC to within the normal range.

Figure 1-2 Schematic of Period 1

*Patients are randomized in a 2:1 ratio to osilodrostat (LCI699) or placebo

** LCI699 Dose determined by Independent Endocrinologists. Intermediate doses may be used in specific circumstances. Please see Section 6.2 for details.

Three 24-hour urine samples will be collected by patients, preferably on consecutive days at screening, immediately prior to Day 1 and the Week 12 visit (primary endpoint) during this study period. Two 24-hour urine samples will be collected, preferably on consecutive days, immediately prior to each of the other visits (i.e. at Weeks 2, 5, and 8).

In order to maintain the treatment blind during Period 1, all laboratory results that may disclose the randomized treatment assignment are blinded to patients, investigators and the Novartis Clinical Trial Team. A group of independent endocrinologists (IEs) is responsible for managing dose titrations during Period 1 between visits. Titrations for patients assigned to placebo will aim to simulate the active arm.

If patients discontinue study drug treatment before the Week 12 visit, Investigators should make reasonable efforts to follow patients and perform assessments for all scheduled visits up to and including the Week 12 visit, even if alternative cortisol lowering therapy has been initiated. During Period 1, the investigator may temporarily interrupt study drug in the event of an AE of suspected adrenal insufficiency, or any AE that requires replacement or stress doses of glucocorticoid therapy.

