1.1.3 Period 2 (Weeks 13-48): single arm, open-label treatment period

Period 2 starts immediately after the Week 12 visit, when the trial becomes open-label with all patients receiving the active drug, osilodrostat. During Period 2 patients randomized to placebo

switch to osilodrostat and undergo their first dose titration with active drug, while patients randomized to osilodrostat continue this treatment and undergo a “second” dose titration.

During Period 2, the investigator is responsible for dose titration. Osilodrostat can be titrated up to a maximum dose of 30 mg b.i.d. during this period. The investigator has access to all laboratory results from the Week 14 assessments onward. The IE does not participate in dose decisions beyond Week 12.

Three 24-hour urine samples will be collected by patients, preferably on consecutive days immediately prior to the Week 36 visit (key secondary endpoint) and Week 48 (end of Core phase), two 24-hour samples will be collected prior to all other visits in Period 2. A patient is considered to have reached a stable efficacious dose when mUFC remains \leq ULN. This dose is continued, unless a change is needed.

1.1.4 Extension phase:

At Week 48, patients have the option to enter a 48 week open-label Extension phase. Patients who do not enter the extension discontinue osilodrostat at Week 48 and conclude with a Post-Treatment (End of Study) visit after 30 days off study drug. Patients who enter the extension phase will continue therapy with osilodrostat for another 48 weeks without interruption. At the end of this extension phase (Week 96), patients will conclude the study with a Post-Treatment (End of Study) visit after 30 days off study drug. During the extension phase the dose of osilodrostat will be maintained at the established effective dose unless a change is required based on mUFC results collected at Weeks 48, 60, 72, and 84. Some patients may remain in the extension phase beyond Week 96, if they are not able to immediately transition to either the long-term follow up study, or to an alternative treatment.

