2.1.1 General definitions

Study drug

Through out the SAP, investigational drug refers to osilodrostat, and study treatment/ study drug refers to osilodrostat or placebo.

Date of study treatment

The start date of study treatment is defined as the first date when a nonzero dose of study treatment was administered and recorded on DAR eCRF. The date of first administration of study treatment in period 1 will be referred as the start date of study treatment.

The last date of study treatment is defined as the last date when a nonzero dose of study drug was administered and recorded on DAR eCRF.

Study day

Study day is used to represent an evaluation, a measurement or an event (e.g. AE onset, laboratory abnormality occurrence, disease progression, etc). The study day is calculated as

Study day = date of assessment –start date of study treatment + 1 (if date of assessment is after start date of study treatment)

Study day = date of assessment –start date of study treatment (if date of assessment is before start date of study treatment)

For any assessment or events such as baseline characteristics or medical history that is supposed to occur prior to start date of the study treatment, study day will be negative. There is no Day 0 defined.

Study day associated with a UFC assessment

The study day associated with a UFC assessment at any particular visit is defined as the study day of the last UFC sample collection for that visit.

Time unit

A year length is defined as 365.25 days. A month length is 30.4375 days (365.25/12). If duration is reported in months, duration in days will be divided by 30.4375. If duration is reported in years, duration in days will be divided by 365.25.

Baseline

Baseline values for efficacy and safety evaluations are defined as the last assessment available before or on the start date of study treatment. If patients have no assessments as defined above, the baseline result will be missing.

Follow up

Regular safety follow-up is scheduled at 30 days after the last date of study treatment. In addition, for patients who discontinued study treatment during Period 1 (Weeks 1 to 12), reasonable efforts should be made to follow the patients and perform the assessments as indicated in protocol visit evaluation schedule table (protocol Table 7-1a) up to and including Week 12. The data collected during the follow up visits in Period 1 will be used as sensitivity analysis for efficacy, and will be used for safety.

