2.14 Interim analysis

The study will have no planned interim analysis for efficacy. The DMC will conduct periodic safety data reviews and dosing review as outlined in DMC charter.

3 Sample size calculation

Eligible patients will be stratified at randomization according to history of pituitary irradiation (yes/no). Based on the LCI699C2201 study, it is assumed that approximately 20% of randomized patients will have a history of pituitary radiation.

With 2:1 randomization ratio, to detect a difference of 45% in complete response rate between 60% in osilodrostat arm and 15% in placebo arm (equivalent odds ratio equals 8.5), a sample size of 42 patients in osilodrostat arm and 21 patients in placebo arm will provide 91% power based on a 1-sided CMH exact test at the 0.025 level. In order to adjust for drop-outs, an additional 10% patients will be enrolled. Thus a total of approximately 69 patients will be enrolled in the study.

The analysis of the key secondary objective will be based on the 2-sided 95% confidence interval constructed using the Clopper-Pearson exact method. If the lower bound of this 95% confidence interval is $\geq 30\%$, the null hypothesis will be rejected and the complete response rate will be considered at least 30% at Week 36. Both the SOM230G2304 trial of Pasireotide LAR and the SOM230B2305 trial of Pasireotide s.c. were powered to show a response rate where the lower bound of the 95% confidence interval was $\geq 15\%$. Therefore an increase in this lower bound of the 95% confidence interval to a threshold of $\geq 30\%$ would provide a significant improvement in clinical benefit to this patient arm.

The above testing on the key secondary objective will only be carried out if the null hypothesis for the primary objective is rejected. This sequential procedure will ensure preservation of the overall 2-sided type 1 error at 5%.

Assuming a 60% complete response rate at Week 36, and less than 50% discontinuation rate of patients in placebo arm prior to Week 12. For the 69 patients in the pooled population, there is higher than 98% chance that the lower bound of 2-side 95% exact CI (based on Clopper-Pearson method) of the observed response rate is larger than 30%.

4 Change to protocol specified analyses

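### The core SAP ends baseline disease duration at the first osilodrostat dose; read as written, this adds about 84 days for placebo patients who switch and gives no value for those who never switch

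*SAP*

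**What the plan says.** Core SAP 2.3.1 (SAP dated 01-Apr-2019) describes the baseline tables for the Full Analysis Set (FAS) and, if different, the Safety Set. Both sets contain placebo patients. On disease duration it says: "Baseline disease characteristics include time to first LCI699 dose since diagnosis of" Cushing's disease. It gives no derivation formula and no separate rule for the placebo arm.

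The footnote to the Period 1 schematic in core SAP 1.1.2 shows what LCI699 means: "Patients are randomized in a 2:1 ratio to osilodrostat (LCI699) or placebo". The protocol's drug overview (1.2.1) likewise gives LCI699 as the research code for osilodrostat.

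Core SAP 2.1.1 has a different term that covers both arms: "investigational drug refers to osilodrostat, and study treatment/ study drug refers to osilodrostat or placebo". It also supplies a date common to both arms: "The date of first administration of study treatment in period 1 will be referred as the start date of study treatment". Its definition of baseline uses that date: "Baseline values for efficacy and safety evaluations are defined as the last assessment available before or on the start date of study treatment".

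Core SAP 1.1.3 says that placebo patients "switch to osilodrostat and undergo their first dose titration with active drug" in Period 2, which begins straight after the Week 12 visit. Core SAP 2.6.3 provides for placebo patients who discontinue in Period 1 and never receive osilodrostat.

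The final SAP (01-Dec-2020), in its own 2.3.1, does not repeat the baseline table, so the core SAP governs it.

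**The concern.** A baseline characteristic should be fixed by the time of randomization or first study dose, and defined in the same way in both arms. Here the end of the interval is first exposure to the active drug. That is Day 1 in one arm and a post-randomization event, about 12 weeks later, in the other. Some placebo patients never reach it.

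A baseline table is read to see who was enrolled and, if it is split by arm, whether the arms are comparable. Under this wording, part of any difference in disease duration would come from the definition. The placebo values would also come only from patients who stayed long enough to start open-label drug.

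**Working it through.** **Inputs**

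- End of the interval: first LCI699 dose (core SAP 2.3.1).
- First osilodrostat dose in the osilodrostat arm: Day 1 (core SAP 1.1.2).
- First osilodrostat dose in the placebo arm: start of Period 2, immediately after the Week 12 visit (core SAP 1.1.3). The exposure formula in core SAP 2.4.1.1 likewise starts Period 2 at that visit.
- Nominal day of the Week 12 visit: Day 85 (core SAP Table 2-1).
- Visit window: ±3 days (protocol 7.1).
- Planned arm sizes: 46 osilodrostat and 23 placebo, 69 in all (core SAP 1.1).
- Month and year lengths: 30.4375 and 365.25 days (core SAP 2.1.1).

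**Step 1: reproduce the visit days.** With no Day 0, nominal day = 7 × week + 1. Weeks 2, 5, 8, 12 and 14 give Days 15, 36, 57, 85 and 99, all as in Table 2-1.

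**Step 2: shift for a placebo patient who switches.** 85 − 1 = 84 days. In other units:

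- 84/7 = 12.0 weeks
- 84/30.4375 = 2.76 months
- 84/365.25 = 0.23 years

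With the window on the Week 12 visit, the range is 84 − 3 = 81 to 84 + 3 = 87 days. The shift in the osilodrostat arm is 0.

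**Step 3: patients with no value.** A placebo patient who stops before the first open-label dose has no LCI699 dose date, so the interval is undefined. The documents give neither an expected nor an observed number. Two planning figures in core SAP Section 3 can be applied as assumptions:

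| Assumption | Arithmetic | Placebo patients with no value |
|---|---|---|
| General 10% drop-out allowance, taken to apply to placebo patients in Period 1 | 0.10 × 23 = 2.3 | about 2 |
| Key secondary power assumption: "less than 50% discontinuation rate of patients in placebo arm prior to Week 12" | 0.50 × 23 = 11.5, not reached | at most 11 |

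The first is an enrolment inflation for the primary test. The second is a ceiling. Neither was set as an estimate of this quantity.

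**Step 4: pooled table.** Section 2.3.1 does not say that the table is split by arm. If all patients are pooled and none drops out, the mean is too high by 84 × 23/69 = 28 days. If 10% of placebo patients have no value, it is too high by 84 × 20.7/(46 + 20.7) ≈ 26 days, and those patients are left out.

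**Step 5: after the change.** If the interval ends at the start date of study treatment, the shift is 0 in both arms. No FAS patient lacks a value because of the definition, since membership requires at least one dose of osilodrostat or placebo (core SAP 2.2.1).

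**The case against.** The strongest reply is that this is a slip of terminology. Section 2.1.1 ties baseline to the start of study treatment, which is the first Period 1 administration of either product. It also treats baseline characteristics as occurring before that date. LCI699 is not itself a defined term there, and 2.3.1 is a list with no formula. A programmer might well have used Day 1 for everyone. That stands as a caution: the documents do not show which date was used, so the consequence is conditional on following the text. It does not rescue the wording. The only literal reading is first osilodrostat dose, and no other section redefines it for placebo patients.

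Three stronger readings are tempting, and the documents do not support them.

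- **That every drop-out lacks a value.** Only placebo patients who stop before their first open-label dose do. Osilodrostat-arm drop-outs and placebo patients who leave later in Period 2 have one.
- **That up to half the placebo arm is expected to be missing.** The figure behind that is a planning ceiling for the key secondary power statement, not a forecast.
- **That the comparison of the arms is compromised.** Disease duration is not the stratification factor (only pituitary irradiation is). It is not among the Per-Protocol Set exclusion criteria, and no analysis names it as a covariate. Section 2.3.1 does not even state that the table is by arm.

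It is also fair to say that 0.23 years is small. The documents give no spread for disease duration, so whether a reader would notice the shift cannot be judged from them.

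**Conclusion.** The rule is wrong as written, and minor. Followed literally, it lengthens disease duration by about 84 days for each placebo patient who switches and leaves it undefined for each placebo patient who never starts osilodrostat. This rests on the nominal visit schedule, on LCI699 meaning osilodrostat, and on the text being programmed as it stands. The number of undefined values is unknown: about 2 and at most 11 of 23 are assumptions, not estimates. The error is systematic and confined to the placebo arm, but it affects a single descriptive variable. The primary and key secondary analyses do not use it.

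**What to change.** In core SAP 2.3.1, replace the phrase with: time from diagnosis of Cushing's disease to the start date of study treatment (as defined in 2.1.1), for all patients. Time to randomization would serve equally well. The first option needs no new definition, and every patient in the FAS and the Safety Set has that date.

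Because the final SAP reports that the baseline summary is already in the interim study report, check which date was used for that table. If it was the first osilodrostat dose, correct the table or add a footnote.

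The cost is one line of SAP wording and, at most, a rerun of one table row. Trial conduct, sample size and inference are unaffected.

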2.3.2 Patient disposition

The number of screened patients and number of patients randomized will be tabulated. The summary will be produced for all pre-screened patients. Reasons for screening failure will be summarized and listed.

Patient disposition will be tabulated for FAS. The summary will include the number of patients who were randomized, treated, ongoing, permanently discontinued from study treatment.

The following summaries will be presented: % is based on total number of FAS patients:

- Number (%) of patients who were randomized (based on data from IRT system)
- Number (%) of patients who were randomized but not treated (based on eCRF DAR page not completed for any study treatment component)
 - Primary reason for not being treated (based on eCRF End of Treatment Phase Completion page)
- Number (%) of patients who were treated (based on eCRF DAR page of each study treatment component completed with non-zero dose administered)
- Number (%) of patients who are still on treatment (based on eCRF End of Treatment Phase page not completed)

- Number (%) of patients who discontinued the study treatment phase (based on eCRF End of Treatment Phase page)
 - Primary reason for study treatment phase discontinuation (based on eCRF End of Treatment Phase Completion page)
 - Number (%) of patients who entered post-treatment follow up
 - Number (%) of patients who discontinued from post-treatment follow-up
 - Primary reason for discontinuation from post-treatment follow-up
 - Number (%) of patients who discontinued in Period 1 (prior to Week 12)
 - Primary reason for discontinuation in Period 1
 - Number (%) of patients who discontinued in Period 2 (Weeks 13 to 48)
 - Primary reason for discontinuation in Period 2
- Number (%) of patients who completed core phase (week 48)
 - Completed Week 48 and did not enter Extension phase
 - Completed Week 48 and entered Extension phase
 - Number (%) of patients who are ongoing in Extension
 - Number (%) of patients who discontinued in the Extension
 - Primary reason for discontinuation in the Extension
 - Number (%) of patients who completed extension

* Patients who completed Week 48 and did not enter extension phase are not counted as discontinuations.

2.3.3 Medical history

Relevant medical history and ongoing medical conditions at baseline will be summarized and listed. The summary will be presented using FAS by primary system organ class (SOC), preferred term (PT), by treatment group and all patients.

2.3.4 Protocol deviations

The number (%) of patients in FAS with any PDs will be tabulated by deviation category (as specified in the study specification document (SSD) by treatment group. Major PDs leading to exclusion from PPS will be tabulated separately by treatment group. All PDs will be listed.

2.4 Treatments (study treatment, rescue medication, concomitant therapies, compliance)

2.4.1 Study treatment / compliance

2.4.1.1 Duration of exposure

The exposure to the study drug will be summarized based on study periods, i.e., period 1 and period 2, and overall period by treatment group.

Period 1 (Week 1 to Week 12)

Duration of exposure (weeks) = (min (date of Week 12 visit – 1, date of last date of study treatment, date of data cut-off, date of death) – date of first date of study treatment + 1)/7

Period 2 (Week 13 to Week 48)

Duration of exposure (weeks) = (min (date of Week 48 visit, date of last date of study treatment, date of data cut-off, date of death) – date of first date of study treatment in period 2 (Week 12 visit) + 1)/7

Overall Period

Duration of exposure (weeks) = (min (date of last date of study treatment, date of data cut-off, date of death) – date of first date of study treatment + 1)/7

In the overall period, the total duration of exposure to study treatment is considered by taking account of the duration of exposure in both Period 1, Period 2, as well as extension. Patients in osilodrostat arm will have exposure only to osilodrostat, and patients in placebo arm will have exposure to both osilodrostat and placebo presented separately.

The above duration calculation includes the periods of temporary interruptions.

Summary of duration of exposure to study treatment will include categorical summaries and continuous summaries using appropriate unit of time.

2.4.1.2 Dose reduction/interruption

The number of patients who have at least one dose reduction or interruption, and the corresponding reasons will be summarized by study period. Although patients may have multiple dose reductions or interruptions with the same reason, patients will be counted only once for each distinct reason.

The total daily dose administered and reason for dose change will be listed with UFC information by date.

2.4.2 Prior, concomitant and post therapies

Concomitant therapy is defined as all interventions (therapeutic treatments and procedures) other than the study treatment administered to a patient coinciding with the study treatment period. Concomitant therapy include medications (other than study drugs) starting on or after the start date of study treatment or medications starting prior to the start date of study treatment and continuing after the start date of study treatment.

Concomitant medications will be coded using the World Health Organization (WHO) Drug Reference Listing (DRL) dictionary that employs the WHO Anatomical Therapeutic Chemical (ATC) classification system and summarized by lowest ATC class and preferred term using frequency counts and percentages. Surgical and medical procedures will be coded using MedDRA and summarized by SOC and preferred term.

All concomitant therapies will be listed. Any concomitant therapies starting and ending prior to the start of study treatment or starting more than 30 days after the last date of study treatment or safety follow-up whichever is later will be flagged in the listing. The safety set will be used for all concomitant medication tables and listings.

Concomitant medications and significant non-drug therapies will be summarized using frequency counts and percentages by ATC class, preferred term and treatment group within each of three study periods: Period 1 (Week 1 to Week 12), Period 2 (Week 13 to Week 48), and overall study period. If a patient discontinued from study in Period 1, the concomitant medications taken during the follow-up period will be summarized in Period 1 and overall period.

